7.4 MedDRA basket

Opportunistic infections

Opportumstic i	in cenons				
Meningomyelitis herpes	Capnocytophaga test positive	Eye infection toxoplasmal	Histoplasmosis disseminated	Mycobacterium ulcerans infection	Pulmonary trichosporonosis
Abscess fungal	Central nervous system fungal infection	Eye infection viral	Human anaplasmosis	Mycotic corneal ulcer	Pulmonary tuberculoma
Acid fast bacilli infection	Central nervous system viral infection	Female genital tract tuberculosis	Human bocavirus infection	Mycotic endophthalmitis	Pulmonary tuberculosis
Acinetobacter bacteraemia	Cerebral aspergillosis	Flavobacterium infection	Human ehrlichiosis	Myocarditis mycotic	Pyelonephritis fungal
Acinetobacter infection	Cerebral candidiasis	Focal epithelial hyperplasia	Human herpesvirus 8 infection	Myocarditis toxoplasmal	Q fever
Acute haemorrhagic conjunctivitis	Cerebral fungal infection	Fungaemia	Indeterminate leprosy	Nasal herpes	Raoultella ornithinolytica infection
Acute hepatitis B	Cerebral toxoplasmosis	Fungal abscess central nervous system	Infection in an immunocompro mised host	Necrotising fasciitis fungal	Renal tuberculosis
Acute hepatitis C	Cervix warts	Fungal cystitis	Intestinal tuberculosis	Necrotising herpetic retinopathy	Respiratory moniliasis
Acute pulmonary histoplasmosis	Chromoblastomy cosis	Fungal endocarditis	Isosporiasis	Neurocryptococc osis	Respiratory tract infection fungal
Adrenal gland tuberculosis	Chronic pulmonary histoplasmosis	Fungal labyrinthitis	JC virus granule cell neuronopathy	Neutropenic infection	Retinitis histoplasma
Aeromonas infection	Coccidioides encephalitis	Fungal oesophagitis	JC virus infection	Neutropenic sepsis	Retinitis viral
Aeromonas test positive	Coccidioidomyc osis	Fungal peritonitis	JC virus test	Nocardia sepsis	Rhodococcus infection
Alcaligenes infection	Colitis herpes	Fungal pharyngitis	JC virus test positive	Nocardia test positive	Rhodococcus test positive
Allescheriosis	Conjunctivitis tuberculous	Fungal retinitis	Joint tuberculosis	Nocardiosis	Salpingitis tuberculous
Alternaria infection	Coxiella infection	Fungal sepsis	Kaposi's sarcoma	Oesophageal candidiasis	Scedosporium infection
Amoebiasis	Creutzfeldt- Jakob disease	Fungal tracheitis	Kaposi's sarcoma AIDS related	Oesophageal tuberculosis	Sepsis pasteurella
Amoebic brain abscess	Cronobacter infection	Fusarium infection	Kaposi's varicelliform eruption	Ophthalmic herpes simplex	Shewanella algae bacteraemia
Amoebic colitis	Cronobacter necrotising enterocolitis	Gastritis fungal	Keratitis fungal	Ophthalmic herpes zoster	Sinusitis aspergillus

TP-GDO-WW-016-01 Effective Date: 28Aug13 Related to: SOP-GDO-WW-019 Confidential

Version 7.0 Version Date: 28NOV2018

Page 53 of 60

Amoebic dysentery	Cryptococcal cutaneous infection	Gastritis herpes	Keratitis viral	Opportunistic infection	Sinusitis fungal
Amoebic lung abscess	Cryptococcal fungaemia	Gastroenteritis cryptococcal	Keratouveitis	Oral candidiasis	Sphingomonas paucimobilis infection
Amoebic skin ulcer	Cryptococcosis	Gastroenteritis cryptosporidial	Laryngitis fungal	Oral fungal infection	Spleen tuberculosis
Anal fungal infection	Cryptococcus test	Gastrointestinal candidiasis	Legionella infection	Oral hairy leukoplakia	Splenic candidiasis
Angina gangrenous	Cryptococcus test positive	Gastrointestinal fungal infection	Lepromatous leprosy	Oral herpes	Splenic infection fungal
Angiostrongylus infection	Cryptosporidiosi s infection	Genital herpes	Leprosy	Oral tuberculosis	Stenotrophomon as infection
Anogenital warts	Cutaneous coccidioidomyco sis	Genital herpes simplex	Leptotrichia infection	Oro-pharyngeal aspergillosis	Stenotrophomon as sepsis
Anorectal human papilloma virus infection	Cutaneous tuberculosis	Genital herpes zoster	Leuconostoc infection	Oropharyngeal candidiasis	Stomatococcal infection
Anti-JC virus antibody index	Cytomegalovirus chorioretinitis	Granulicatella bacteraemia	Listeria encephalitis	Oropharyngitis fungal	Stomatococcus test positive
Arthritis fungal	Cytomegalovirus colitis	Granulicatella infection	Listeria sepsis	Orthopox virus infection	Strongyloidiasis
Aspergilloma	Cytomegalovirus duodenitis	Hepatic candidiasis	Listeria test positive	Osteomyelitis blastomyces	Superinfection fungal
Aspergillosis oral	Cytomegalovirus enteritis	Hepatic infection fungal	Listeriosis	Osteomyelitis fungal	Superinfection mycobacterial
Aspergillus infection	Cytomegalovirus enterocolitis	Hepatitis B	Lower respiratory tract herpes infection	Otitis media fungal	Systemic candida
Aspergillus test	Cytomegalovirus gastritis	Hepatitis C	Lower respiratory tract infection fungal	Pancreatitis fungal	Systemic mycosis
Aspergillus test positive	Cytomegalovirus gastroenteritis	Hepatitis toxoplasmal	Lower respiratory tract infection viral	Pantoea agglomerans infection	Thyroid tuberculosis
Atypical mycobacterial infection	Cytomegalovirus gastrointestinal infection	Hepatosplenic candidiasis	Lupus vulgaris	Paracoccidioides infection	Tonsillitis fungal
Atypical mycobacterial lower respiratory tract infection	Cytomegalovirus gastrointestinal ulcer	Herpes oesophagitis	Lymph node tuberculosis	Parasitic encephalitis	Toxoplasmosis
Atypical mycobacterial lymphadenitis	Cytomegalovirus hepatitis	Herpes ophthalmic	Lymphadenitis fungal	Parvimonas infection	Tuberculoid leprosy
Atypical mycobacterial pneumonia	Cytomegalovirus infection	Herpes pharyngitis	Male genital tract tuberculosis	Parvimonas micra infection	Tuberculoma of central nervous system

Confidential

Version 7.0 Version Date: 28NOV2018

Page 54 of 60

Atypical mycobacterium pericarditis	Cytomegalovirus mucocutaneous ulcer	Herpes sepsis	Meningitis aspergillus		
Atypical pneumonia	Cytomegalovirus myelomeningora diculitis	Herpes simplex	Meningitis candida	Penicillium infection	Tuberculosis bladder
Babesiosis	Cytomegalovirus myocarditis	Herpes simplex cervicitis	Meningitis coccidioides	Pericarditis fungal	Tuberculosis gastrointestinal
Bacillary angiomatosis	Cytomegalovirus oesophagitis	Herpes simplex colitis	Meningitis cronobacter	Pericarditis histoplasma	Tuberculosis liver
Balamuthia infection	Cytomegalovirus pancreatitis	Herpes simplex encephalitis	Meningitis cryptococcal	Pericarditis tuberculous	Tuberculosis of central nervous system
BK virus infection	Cytomegalovirus pericarditis	Herpes simplex gastritis	Meningitis exserohilum	Peritoneal candidiasis	Tuberculosis of eye
Blastocystis infection	Cytomegalovirus syndrome	Herpes simplex hepatitis	Meningitis fungal	Peritoneal tuberculosis	Tuberculosis of genitourinary system
Blastomycosis	Cytomegalovirus test	Herpes simplex meningitis	Meningitis herpes	Phaehyphomyco sis	Tuberculosis of intrathoracic lymph nodes
Bone tuberculosis	Cytomegalovirus test positive	Herpes simplex meningoencepha litis	Meningitis histoplasma	Pharyngeal abscess	Tuberculosis of peripheral lymph nodes
Borderline leprosy	Cytomegalovirus urinary tract infection	Herpes simplex meningomyelitis	Meningitis listeria	Pneumocystis jirovecii infection	Tuberculosis ureter
Botryomycosis	Cytomegalovirus viraemia	Herpes simplex necrotising retinopathy	Meningitis toxoplasmal	Pneumocystis jirovecii pneumonia	Tuberculous abscess central nervous system
Bovine tuberculosis	Dengue fever	Herpes simplex oesophagitis	Meningitis tuberculous	Pneumocystis test positive	Tuberculous endometritis
Brachyspira infection	Disseminated Bacillus Calmette-Guerin infection	Herpes simplex otitis externa	Meningoencepha litis herpes simplex neonatal	Pneumonia blastomyces	Tuberculous laryngitis
Brevibacterium infection	Disseminated cryptococcosis	Herpes simplex pharyngitis	Meningoencepha litis herpetic	Pneumonia cryptococcal	Tuberculous pleurisy
Bronchitis fungal	Disseminated cytomegaloviral infection	Herpes simplex pneumonia	Meningoencepha litis viral	Pneumonia cytomegaloviral	Tuberculous tenosynovitis
Bronchopulmona ry aspergillosis	Disseminated tuberculosis	Herpes simplex sepsis	Methylobacteriu m infection	Pneumonia fungal	Upper respiratory fungal infection
Burkholderia cepacia complex infection	Disseminated varicella zoster vaccine virus infection	Herpes simplex visceral	Microsporidia infection	Pneumonia herpes viral	Urinary tract infection fungal

Confidential

Version 7.0 Version Date: 28NOV2018

Page 55 of 60

Burkholderia cepacia complex sepsis	Ear tuberculosis	Herpes virus infection	Miliary Pneumonia pneumonia legionella		Variant Creutzfeldt- Jakob disease
Burkholderia gladioli infection	Encephalitis cytomegalovirus	Herpes zoster	Mucocutaneous candidiasis	Pneumonia toxoplasmal	Varicella
Burkholderia infection	Encephalitis fungal	Herpes zoster cutaneous disseminated	Mucormycosis	Polyomavirus- associated nephropathy	Varicella keratitis
Burkholderia mallei infection	Encephalitis post varicella	Herpes zoster disseminated	Mycetoma mycotic	Porphyromonas infection	Varicella zoster gastritis
Burkholderia pseudomallei infection	Endocarditis candida	Herpes zoster infection neurological	Mycobacterial infection	Presumed ocular histoplasmosis syndrome	Varicella zoster oesophagitis
Burkholderia test positive	Endocarditis histoplasma	Herpes zoster meningitis	Mycobacterial peritonitis	Progressive multifocal leukoencephalop athy	Varicella zoster pneumonia
Candida endophthalmitis	Endocarditis Q fever	Herpes zoster meningoencepha litis	Mycobacterium abscessus infection	Progressive vaccinia	Varicella zoster virus infection
Candida infection	Enterocolitis fungal	Herpes zoster meningomyelitis	Mycobacterium avium complex immune restoration disease	Prostatitis tuberculous	Viral keratouveitis
Candida osteomyelitis	Epididymitis blastomyces	Herpes zoster necrotising retinopathy	Mycobacterium avium complex infection	Pseudallescheria infection	Viral myelitis
Candida pneumonia	Epididymitis tuberculous	Herpes zoster oticus	Mycobacterium chelonae infection	Pseudallescheria sepsis	Viral oesophagitis
Candida retinitis	Exserohilum infection	Herpes zoster pharyngitis	Mycobacterium fortuitum infection	Pseudomonal sepsis	Viral sepsis
Candida sepsis	Extrapulmonary tuberculosis	Histoplasmosis	Mycobacterium kansasii infection	Pseudomonas aeruginosa meningitis	Viral uveitis
Capnocytophaga infection	Eye infection fungal	Histoplasmosis cutaneous	Mycobacterium marinum infection	Pulmonary mycosis	Yersinia sepsis

7.5 Laboratory Data Conversion and Transformation Rules

• Conversion to Système International (SI) Units

Laboratory data should be stored on the database in the units in which they were originally delivered by the laboratory.

For analysis and reporting purposes, the data will be converted to SI units to allow the comparison of data delivered in different original units.

Results that include inequality sign will be converted into a numeric form removing inequality sign.

TP-GDO-WW-016-01 Confidential Version 7.0 Effective Date: 28Aug13 Version Date: 28NOV2018 Related to: SOP-GDO-WW-019

Page 56 of 60

Results that cannot be converted into an expected numeric form nor interpreted, such as alphabetic entries like "adequate", will usually not be further processed, but displayed in patient listings.

Marked Laboratory Abnormalities

For each laboratory test, a Marked Abnormality Range has been defined. A value outside of this range is considered to be potentially clinically relevant. This Marked Abnormality Range is wider than the Reference Range.

In addition, for each laboratory test, a percentage change, as an increase and/or decrease, has been defined which represents a clinically relevant change from baseline.

A Marked Abnormality is therefore defined as a test result:

which is outside of the Marked Abnormality Range, and which also represents a clinically relevant change from baseline of at least the designated amount during or within 30 days after end of trial treatment.

Baseline is taken as the last valid value before starting treatment. If no baseline is available, the midpoint of the Reference Range will be substituted for processing purposes for determination of Marked Abnormalities.

For urinalysis a missing baseline value will be replaced by 0 (zero).

NOTE: For calculating means and mean changes over time, missing values will not be included. If no baseline is available, no change from baseline will be calculated.

Values above and below the Reference Range are flagged on the listing by H and L. respectively. Marked Abnormalities are flagged by HH or LL.

Reference Ranges

Related to: SOP-GDO-WW-019

TP-GDO-WW-016-01 Confidential Version 7.0 Effective Date: 28Aug13 Version Date: 28NOV2018

Page 57 of 60

Laboratory Test Class	Laboratory Test	SI Unit	Reference Range [1,2]	Marked Abnormality Range	Direction of Change	Relevant Change from Baseline
Hematology	Hematocrit	fraction	M: 0.37 – 0.49 F: 0.36 – 0.46 b	0.31 - 0.56	Increase Decrease	≥ 15% ≥ 15%
	Hemoglobin	g/L	M: 130 – 180 F: 120 – 160 b	110-200	Increase Decrease	≥ 15% ≥ 15%
	Leukocytes (WBC)	10°/L	4.5 – 11.0	3.0 - 18.0	Increase Decrease	≥ 30% ≥ 30%
	Platelets	10 ⁹ /L	150 - 350	100 - 550	Increase Decrease	≥ 50% ≥ 30%
	Mean corpuscular hemoglobin (MCH)	pg/cell	25.0 - 35.0	21.2 - 40.2	Increase Decrease	≥ 15% ≥ 15%
	Mean corpuscular hemoglobin concentration (MCHC)	g/L	310 – 370	260 – 430	Increase Decrease	≥ 15% ≥ 15%
	Mean corpuscular volume (MCV)	tl.	78 – 100	66 - 115	Increase Decrease	≥ 15% ≥ 15%
	Erythrocytes (RBC)	10 ¹² /L	M: 4.50 – 5.30 F: 4.10 – 5.10 b	3.80 - 6.10	Increase Decrease	≥ 15% ≥ 15%
Differentials	Bands	109/L	0-0.70	0-1.40	Increase	≥ 30%
	Bands	fraction	0 - 0.05	0 - 0.10	Increase	≥ 30%
	Basophils	109/L	0-0.20	0 - 0.40	Increase	≥ 100%
	Basophils	fraction	0-0.03	0 - 0.06	Increase	≥ 100%
	Lymphocytes	10°/L	1.00 - 4.80	0.70 - 7.60	Increase Decrease	≥ 30% ≥ 30%
	Lymphocytes	fraction	0.16 - 0.46	0.10 - 0.72	Increase Decrease	≥ 30% ≥ 30%
	Monocytes	109/L	0 - 0.80	0 - 1.70	Increase	≥ 100%
	Monocytes	fraction	0-0.11	0-0.22	Increase	≥ 100%
	Neutrophils	10 ⁹ /L	1.80 - 7.70	1.50 - 9.25	Increase Decrease	≥ 20% ≥ 20%
	Neutrophils	fraction	0.45 - 0.75	0.37 - 0.90	Increase Decrease	≥ 20% ≥ 20%
	Eosinophils	10°/L	0-0.45	0-0.90	Increase	≥ 100%
	Eosinophils	fraction	0 - 0.08	0-0.16	Increase	≥ 100%
Coagulation	Prothrombin Time, normalized ratio (PTINR)	ratio	0.70 - 1.30	≤ 2.00	Increase	≥ 30%
	Partial Thromboplastin Time, activated (PTT)	seconds	22.1 - 34.1	0-45	Increase	≥ 40%
	Fibrinogen	g/L	1.75 - 4.00 a	≥ 1.30	Decrease	≥30%
	Antithrombin 3	fraction	0.80 - 1.30	≥ 0.60	Decrease	≥ 20%
Heart Function	ASAT (SGOT)	U/L	M: 0-40° F: 0-25 ^b	0-80	Increase	≥ 50%
	Lactic Dehydrogenase (LDH)	U/L	0-210°	0-420	Increase	≥ 50%
	Creatine phosphokinase (CPK) total	U/L	M: 60 – 400 ^a F: 40 – 150 ^b	≤ 800	Increase	≥ 50%
	CPK (MB Fraction)	μg/L	0-5°	< 5	Increase	0%

Laboratory Test Class	Laboratory Test	SI Unit	Reference Range [1,2]	Marked Abnormality Range	Direction of Change	Clinically Relevant Change from Baseline
Liver Function	Alkaline Phosphatase	U/L	M: 0 - 115° F: 0 - 100°	0-220	Increase	≥ 50%
	ALAT (SGPT)	U/L	M: 0-55° F: 0-30°	0-110	Increase	≥ 50%
	Total Bilirubin	μmol/L	0-17°	0-34	Increase	≥ 75%
	Direct bilirubin	μmol/L	0-7°	0-14	Increase	≥ 75%
	γ-GTP	U/L	M: 0 - 94° F: 0 - 70°	0-190	Increase	≥ 50%
Renal Function	BUN	mmol/L	2.9 - 8.9	0 - 14.3	Increase	≥ 50%
	Creatinine	μmol/L	0-133	0-154	Increase	≥ 50%
Thyroid	Triiodothyronine (T3)	nmol/L	0.92 - 2.78	0.74 - 3.30	Increase Decrease	≥ 20% ≥ 20%
Function	Thyroxine (T4)	nmol/L	58 - 140	30 - 164	Increase Decrease	≥ 20% ≥ 20%
	Free T4	pmol/L	10 – 36	5-40	Increase Decrease	≥ 20% ≥ 20%
	TSH	mU/L	0-5.0°	0-10.0	Increase	≥ 30%
Protein	Albumin	g/L	35.0 - 55.0	≥ 30	Decrease	≥ 20%
	Total Protein	g/L	60 - 80	55 - 87	Increase Decrease	≥ 20% ≥ 20%
Lipid	Triglycerides (fasting)	mmol/L	0.45 - 1.69	0-2.83	Increase	≥ 100%
Chemistry	Cholesterol	mmol/L	0-6.18	0-8.30	Increase	≥ 30%
	LDL-Cholesterol	mmol/L	0-4.13	0-5.4	Increase	≥ 30%
	HDL-Cholesterol	mmol/L	≥ 0.91	≥ 0.65	Decrease	≥ 30%
Electrolytes	Chloride	mmol/L	100 - 108	95 – 115	Increase Decrease	≥ 7% ≥ 7%
	Potassium	mmol/L	3.4-4.8	2.9 – 5.8	Increase Decrease	≥ 20% ≥ 20%
	Sodium	mmol/L	135 – 145	130-150	Increase Decrease	≥ 7% ≥ 7%
	Bicarbonate	mmol/L	22 – 26	18 – 28	Increase Decrease	≥ 20% ≥ 20%
	Calcium	mmol/L	2.10 - 2.60	2.00 - 2.90	Increase Decrease	≥ 10% ≥ 10%
	Phosphorus inorganic	mmol/L	0.84 - 1.45	0.75 - 1.60	Increase Decrease	≥ 30% ≥ 30%
	Blood Glucose (fasting)	mmol/L	3.90 - 6.10	2.80 - 11.10	Increase Decrease	≥ 75% ≥ 75%
	Uric Acid	μmol/L	M: 214 – 506 F: 137 – 393 b	0-600	Increase	≥ 50%
Urinalysis	Proteinuria	1 to 6	1-3	1-3	Increase	≥ 2 units ^d
Dipstick	Glycosuria	1 to 6	1-3	1-3	Increase	≥ 2 units d
	Hematuria	1 to 6	1-3	1 – 3	Increase	≥ 2 units d
	Leukocyturia	1 to 6	1-3	1-3	Increase	≥ 2 units d
Urinalysis	Casts	/HPF	0-2	0-2	Increase	≥ 2 units
Microscopic e	WBCs	/HPF	0-2	0-2	Increase	≥ 2 units
	RBCs	/HPF	0-2	0-2	Increase	≥ 2 units
	Urinary spec. gravity f	No unit	1.001 - 1.035	not defined	not defined	not defined

- a) For reporting and analyzing, the data are linearly transformed to the Reference Range according to the formula below.
- b) For reporting and analyzing, the data for females are linearly transformed to the Reference Range

- for males according to the formula below.
- c) For reporting and analyzing, the data are linearly transformed to the Reference Range according to the formula below.
 - To prevent transformed values becoming negative, the investigator lower limit is replaced by zero.
- d) Note that baseline values of 5 and 6 do not allow a subsequent clinically relevant change.
- e) To be done if dipstick is positive and microscopic examination needed for specific quantitation/confirmation.
- f) Specific gravity is a measurement of solute load in the urine. It is increased markedly by both proteinuria and glycosuria.

A value > 1.030 in the absence of proteinuria or glycosuria is most commonly caused by radiographic contrast. In volume depletion specific gravity is usually >1.020. A fixed value of 1.010 (isosthenuria) is characteristic of chronic renal impairment. A fixed value of 1.000 - 1.005 occurs in diabetes insipidus. Specific gravity has an important influence on urine microscopy because cells lyse more rapidly in dilute urine, which may lead to considerable inaccuracies in quantitation of cells. Cells swell and rupture in dilute urine and shrink in concentrate urine. Casts are rarely seen at low urine osmolality [5].

Conclusion: increase or decrease in urine specific gravity clinically relevant in context with other parameters from urinalysis.

Note: The following modification is applied to creatinine and TSH as needed.

Creatinine: The transformation of data described above as c) is applied for only Japanese patients study as needed.

TSH: The lower limit of the reference range and Marked Abnormal Range are modified and Clinically Relevant Change from Baseline for decrease is provided as needed.

• Formula for Linear Transformation

$$R_T = S_L + [(R_U - I_L) / (I_H - I_L)]*(S_H - S_L)$$

R_T: transformed value

R_U: untransformed value

Related to: SOP-GDO-WW-019

I_L: IH investigator limits, low and high

S_L: SH reference limits, low and high

For female to male transformation replace I_L , I_H by the reference limits for female, and S_L , S_H by the reference limits for male.

7.6 Rule for summary of titer for anti AQP4 antibody status

Titer for anti AQP4 antibody status except screening visit will be replaced by following rule. This rule will apply to throughout TFL.

- If value is "<16", value will be replaced as 4.
- If titer is character (e.g. ">16384", ">65536" except "<16") or titer is numeric more than 16384 (e.g. "65536", "262144"), value will be replaced as 65536.

TP-GDO-WW-016-01 Confidential Version 7.0 Effective Date: 28Aug13 Version Date: 28NOV2018

Page 60 of 60

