4.12 Pharmacokinetics and Pharmacodynamics

TP-GDO-WW-016-01 Confidential Version 7.0 Effective Date: 28Aug13 Version Date: 28NOV2018

Related to: SOP-GDO-WW-019

Version Date: 28NOV2018

Page 33 of 60

The serum SA237 concentrations will be reported using the PK-PPS. The PD variables (IL-6, sIL-6R, hsCRP, anti-AQP4Ab, Plasmablast) will be reported using the SAF population.

To determine concentrations of SA237, serum samples will be drawn at various time points throughout the study. At Week 0, blood specimens for PK and PD samples will be collected prior to first dose administration of study drug (blank value). At other visits, PK and PD samples will be collected along with hematology samples at any time prior to drug administration according to the Schedule of Study assessments.

To support the Japanese BLA, the following reports will be produced. SA237 concentrations and PD variables in serum will be listed and summarized using descriptive statistics (including geometric mean and CV%, arithmetic mean and SD, median, observed maximums and minimums, and sample size). Arithmetic mean ± SD serum concentration-time profile and combined all subjects' serum concentration-time profiles (spaghetti plot) will be plotted using linear and semi-log scale. In addition, individual serum concentration-time profile will be plotted for each subjects using linear and semi-log scale. Summary tables and figures of SA237 concentration and PD variables will be provided as follows:

Concentration of SA237 and PD variables (absolute values as well as change from baseline) in serum will be summarized using descriptive statistics and arithmetic mean \pm SD serum concentration-time profile will be plotted by following subgroup using linear scale.

Samples that were excluded from the summary statistics will be marked in the listing.

The rule for summary of titer for anti AQP4 antibody status is defined in appendix 7.6.

Summary tables, figures, and listings of SA237 concentration and PD variables will be provided as follows:

- Summaries of concentrations of SA237 by visit will be presented by age category, Japanese/non-Japanese, relapse/no-relapse, ADA status, and overall.
- Summary of concentration of IL-6, sIL-6R, and hsCRP by visit will be presented by age category, Japanese/non-Japanese, relapse/no-relapse and overall in each of treatment group.

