- A by-subject spaghetti plot of the absolute value for titer of anti-AQP4 antibody, Plasmablast (Plasmablasts/CD19+ (%), Plasmablasts/CD45+ (%), and Plasmablasts (cells/uL)), and CD19+ cells (CD19+/CD45+ (%), and CD19+ (cells/uL)) by treatment group in each subgroup (NMO/NMOSD and AQP4 Status, relapse/no-relapse) using linear scale.
- An Arithmetic mean \pm SD plot of concentration for SA237 in serum by subgroup (age category, Japanese/non-Japanese, relapse/no-relapse, ADA status) using linear scale and overall using linear and semi log scale.
- An Arithmetic mean ± SD plot of the absolute value and the change from baseline for concentration of IL-6, sIL-6R, and hsCRP by treatment group using linear and semilog scale.

TP-GDO-WW-016-01 Confidential Version 7.0 Effective Date: 28Aug13 Version Date: 28NOV2018

Page 36 of 60

- An Arithmetic mean ± SD plot of the absolute value for concentration of IL-6, sIL-6R, and hsCRP by subgroup (age category, Japanese/non-Japanese, relapse/no-relapse, ADA status) in each of treatment group using linear scale.
- An Arithmetic mean ± SD plot of the absolute value for concentration of IL-6, sIL-6R, and hsCRP by treatment group in each subgroup (age category, Japanese/non-Japanese, relapse/no-relapse, ADA status) using linear scale
- An Arithmetic mean ± SD plot of the absolute value for titer of anti-AQP4 antibody, Plasmablast (Plasmablasts/CD19+ (%), Plasmablasts/CD45+ (%), Plasmablasts (cells/uL)), and CD19+ cells (CD19+/CD45+ (%) and CD19+ (cells/uL)) by treatment group using linear and semi-log scale
- An Arithmetic mean ± SD plot of the absolute value for titer of anti-AQP4 antibody, Plasmablasts (Plasmablasts/CD19+ (%), Plasmablasts/CD45+ (%), Plasmablasts (cells/uL)), and CD19+ cells (CD19+/CD45+ (%) and CD19+ (cells/uL)) by subgroup (NMO/NMOSD and AQP4 Status, relapse/no-relapse) in each of treatment group using linear scale
- An Arithmetic mean ± SD plot of the absolute value for titer of anti-AQP4 antibody, Plasmablast (Plasmablasts/CD19+ (%), Plasmablasts/CD45+ (%), Plasmablasts (cells/uL)), and CD19+ cells (CD19+/CD45+ (%) and CD19+ (cells/uL)) by treatment group in each subgroup (NMO/NMOSD and AQP4 Status, relapse/no-relapse) using linear scale.
- A by-subject listing of actual doses, date and time of sampling, visit, relative day, and the accession number.

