- Scatter plot of anti-AQP4 antibody titer versus plasmablast (Plasmablasts/CD19+ Plasmablasts/CD45+ (%), Plasmablasts (cells/uL)) will be presented at Weeks 0, 2 and 4, 8, 12, 24, and Q24W. When the data of anti-AQP4 antibody is negative, put "1" as a titer for negative samples and replace to "BLQ".
- Scatter plots of serum SA237 concentration versus body weight at weeks 2, 4, Q4W respectively.

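### Anti-AQP4 titre summaries: the cap at 65536 hides measured changes above 16384, and change from baseline is taken as a raw difference rather than a fold change (descriptive outputs only; low priority)

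*SAP*

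**What the plan says.** SAP Appendix 7.6 sets out the replacement rule: "Titer for anti AQP4 antibody status except screening visit will be replaced by following rule". At the lower end, "If value is '<16', value will be replaced as 4". At the upper end there are two triggers with the same result. One concerns open-ended results: "If titer is character (e.g. '>16384', '>65536' except '<16"). The other concerns measured ones: if "titer is numeric more than 16384 (e.g. '65536', '262144'), value will be replaced as 65536". On scope it adds: "This rule will apply to throughout TFL". Read literally, that covers the by-subject titre listing planned in SAP 4.12 as well as tables and figures.

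SAP 4.12 counts anti-AQP4 antibody among the PD variables and plans: "Concentration of SA237 and PD variables (absolute values as well as change from baseline) in serum will be summarized using descriptive statistics". The statistics listed there include geometric mean and CV%, arithmetic mean and SD, and the median. Figures include individual line plots of titre, both as level and as change from baseline, on linear and semi-log axes, and "An Arithmetic mean ± SD plot of the absolute value for titer of anti-AQP4 antibody". For the scatter plot of titre against plasmablasts, the instruction for negatives is: "put '1' as a titer for negative samples and replace to 'BLQ".

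Neither 4.12 nor 7.6 defines a log or ratio change for this titre.

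**The concern.** There are two separate defects. The first is loss of information. The rule itself names 262144 as a value that can occur, then overwrites it. Changes between 65536 and 262144 disappear in both directions, and no planned post-screening output would show the measured value.

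The second is the scale. The values named in the rule (16, 16384, 65536, 262144) are all powers of four, so the titre appears to move in four-fold steps. A raw difference weights each step by the starting titre, and two of the planned presentations of change do not exist for a patient whose titre falls or stays the same.

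What is at stake is the reading of a mechanistic marker. SAP 4.14 and Protocol 6.2 argue that a reduction in anti-AQP4 antibody is needed before relapses are prevented, and use this to justify a hazard ratio of 1.0 for the first two months. A reader checking that reasoning would turn to the titre outputs.

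**Working it through.** **Inputs.** The replacement rule comes from SAP 7.6 and the summary statistics from SAP 4.12. The documents state no figure that can be reproduced here.

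**Step 1: apply the rule to pairs of titres.** Recorded change = recorded follow-up − recorded baseline.

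| Measured baseline → follow-up | Recorded as | True fold | Recorded fold | Recorded change |
|---|---|---|---|---|
| 262144 → 65536 | 65536 → 65536 | 4 down | none | 0 |
| 65536 → 262144 | 65536 → 65536 | 4 up | none | 0 |
| 262144 → 16384 | 65536 → 16384 | 16 down | 4 down | −49152 |
| 65536 → 16384 | unchanged | 4 down | 4 down | −49152 |
| 1024 → 256 | unchanged | 4 down | 4 down | −768 |
| 256 → 64 | unchanged | 4 down | 4 down | −192 |

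These rows need no assumption about patients.

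**Step 2: weight on the raw scale.** For the same 4-fold fall, 49152 / 768 = 64 and 49152 / 192 = 256. One patient starting at 65536 counts as much as 64 patients starting at 1024, or 256 starting at 256.

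**Step 3: which listed statistics exist for change.** A geometric mean needs positive values, and so does a log axis. A fall gives a negative difference and a stable titre gives zero. The geometric mean of change and the semi-log change plot are therefore undefined for these patients. The arithmetic mean and the median remain, and only the median escapes the weighting in Step 2.

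**Step 4: illustration of dominance (assumed titres).** Of 90 patients randomised 2:1, 60 are on satralizumab. With seronegatives at their 30% limit and spread evenly across arms, 60 × 0.70 = 42 are seropositive. Suppose all 42 fall 4-fold, k of them start at 65536 and the rest at a typical titre m. The share of the mean change from the k patients is k × 49152 / [k × 49152 + (42 − k) × 0.75 × m].

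| m | k = 1 | k = 4 | Median change |
|---|---|---|---|
| 64 | 96% | 99% | −48 |
| 256 | 86% | 96% | −192 |
| 1024 | 61% | 87% | −768 |
| 4096 | 28% | 63% | −3072 |

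**Step 5: what the cap does to dominance.** With one patient at 262144 and 41 at 1024, that patient's share of the baseline mean is 65536 / (65536 + 41 × 1024) = 61% capped, against 262144 / (262144 + 41 × 1024) = 86% uncapped. If all 42 fall 4-fold, this patient adds 0 to the capped mean change. So the cap reduces dominance; the raw scale creates it.

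**Step 6: what the cap does to a ratio summary.** If k of 42 start at 262144 and all fall 4-fold, the capped geometric mean ratio is 0.25^((42 − k)/42): 0.258, 0.267 and 0.285 for k = 1, 2 and 4, against a true 0.250. A log scale alone does not undo the cap, but the distortion is modest in these examples.

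**Step 7: negatives.** Appendix 7.6 gives `<16` the value 4; the scatter plot in 4.12 gives negatives the value 1. If `<16` is how a negative is reported (implied, not stated), the two differ by one four-fold step.

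**The case against.** The cap has a plausible purpose. Appendix 7.6 lists `>16384`, `>65536`, 65536 and 262144 together, so results seem to arrive with different upper reporting limits. A common ceiling stops a change of limit from looking like a change of titre. A patient reported as `>16384` at one visit and 262144 at the next has an undetermined change; substituting 16384 would show a false 16-fold rise. The SAP does not give this reason, but it stands as a reason not to keep all numeric titres beside open-ended ones without a censoring method.

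The plan also offers more than the arithmetic mean: the median, geometric means of levels (whose ratio between visits gives a fold change) and semi-log plots of absolute titre. Plasmablasts, the earlier step in the stated mechanism, are summarised and plotted too. A reader might infer that the titre outputs will conceal the mechanism; the documents do not support that. Nor do they support the inference that the cap makes a few patients dominate the mean, since Step 5 shows the opposite.

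The Protocol Version 10 rationale reports drift in the cell-based assay and a move to ELISA, so keeping every recorded step would not by itself make long-term titres reliable. This does not remove the point: 7.6 names no assay, and Protocol Appendix 1, Table 6 still allows either method after screening.

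Finally, titre is descriptive and lies outside the testing hierarchy in SAP 4.10.1.4. That stands in full and sets the priority.

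**Conclusion.** Both defects hold, as descriptive defects only. From the rule alone, measured changes between 65536 and 262144 are recorded as zero, and 262144 to 16384 is recorded as 4-fold instead of 16-fold. From the choice of scale alone, the arithmetic mean change weights a patient at 65536 64 times as heavily as one at 1024 for the same fold fall, and the geometric mean and semi-log plot of change fail for zero or negative changes. This assumes that change from baseline means a simple difference, as no other definition is given.

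The shares of 28% to 99% in Step 4 illustrate assumed titres and are not estimates for this trial. It would also be wrong to say that every titre is altered: screening values are exempt, so the subgroups by AQP4 status at screening (SAP 4.10.1.5) are untouched. No hypothesis test or efficacy endpoint uses the capped values. Priority is low.

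**What to change.** - **Scale (SAP 4.12).** Report change as log4 or ratio to baseline, by arm and visit: median, geometric mean ratio, and number of patients with at least a 4-fold fall. SAP 4.13 already uses a four-fold criterion and a titre ratio to baseline for anti-drug antibodies.
- **Listing (SAP 7.6).** Exempt the by-subject listing from the replacement rule, so that titres appear as measured.
- **Cap (SAP 7.6).** Keep a common ceiling for the main summary and state the reason. Show the number of values at or above the cap by arm and visit. Add a sensitivity summary using measured values, with `>x` results treated as right-censored at x and the censored-data method named.
- **Negatives.** Use one value in 7.6 and in the scatter plot of 4.12, and state whether `<16` means negative.

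The cost is SAP wording and a little programming, mostly for the censored sensitivity summary. No new data are needed.
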